**6.1.1.2 Serious Adverse Events**

If an AE meets any of the following criteria, it is to be reported to AbbVie as an SAE within 24 hours of the site being made aware of the SAE.

**Death of Subject**

An event that results in the death of a subject.

---

Life-Threatening	An event that, in the opinion of the Investigator, would have resulted in immediate fatality if medical intervention had not been taken. This does not include an event that would have been fatal if it had occurred in a more severe form.
Hospitalization or Prolongation of Hospitalization	An event that results in an admission to the hospital for any length of time or prolongs the subject's hospital stay. This does not include an emergency room visit or admission to an outpatient facility.
Congenital Anomaly	An anomaly detected at or after birth, or any anomaly that results in fetal loss.
Persistent or Significant Disability/Incapacity	An event that results in a condition that substantially interferes with the activities of daily living of a study subject. Disability is not intended to include experiences of relatively minor medical significance such as headache, nausea, vomiting, diarrhea, influenza, and accidental trauma (e.g., sprained ankle).
Important Medical Event Requiring Medical or Surgical Intervention to Prevent Serious Outcome	An important medical event that may not be immediately life-threatening or result in death or hospitalization, but based on medical judgment may jeopardize the subject and may require medical or surgical intervention to prevent any of the outcomes listed above (i.e., death of subject, life-threatening, hospitalization, prolongation of hospitalization, congenital anomaly, or persistent or significant disability/incapacity). Additionally, any elective or spontaneous abortion or stillbirth is considered an important medical event. Examples of such events include allergic bronchospasm requiring intensive treatment in an emergency room or at home, blood dyscrasias or convulsions that do not result in inpatient hospitalization, or the development of drug dependency or drug abuse.

For SAEs with the outcome of death, the date and cause of death will be recorded on the appropriate case report form.

---

### **6.1.2 Adverse Event Severity**

The Investigator will use the following definitions to rate the severity of each AE:

- |                 |  |
|-----------------|--|
| Mild     | The AE is transient and easily tolerated by the subject.   |
| Moderate | The AE causes the subject discomfort and interrupts the subject's usual activities.  |
| Severe   | The AE causes considerable interference with the subject's usual activities and may be incapacitating or life-threatening. |

### **6.1.3 Relationship to Study Drug**

The Investigator will use the following definitions to assess the relationship of the AE to the use of study drug(s) (causality will be assessed for both ADA and MTX):

- |                                  |  |
|----------------------------------|--|
| Reasonable Possibility    | An AE where there is evidence to suggest a causal relationship between the study drug and the AE.    |
| No Reasonable Possibility | An AE where there is no evidence to suggest a causal relationship between the study drug and the AE. |

For causality assessments, events assessed as having a reasonable possibility of being related to the study drug(s) will be considered "associated." Events assessed as having no reasonable possibility of being related to study drug(s) will be considered "not associated". In addition, when the Investigator has not reported a causality or deemed it not assessable, AbbVie will consider the event associated.

If an Investigator's opinion of no reasonable possibility of being related to study drug(s) is given, an "Other" cause of event must be provided by the Investigator for the SAE.

### **6.1.4 Adverse Event Collection Period**

[figure not shown]
All AE reported from the time of study drugs administration until 70 days following discontinuation of study drugs administration have elapsed will be collected, whether solicited or spontaneously reported by the subject. In addition, SAEs and protocol related

non-serious AEs will be collected from the time the subject signed the study-specific informed consent. AE information will be collected and recorded on the appropriate eCRF.

Subjects will be contacted approximately 70 days following study drug (ADA) discontinuation for an assessment of any new or ongoing AEs, except those subjects that continue on ADA therapy after the end of study participation. These subjects are not required to complete the 70-day follow-up and any new AEs should be reported through the mechanism used for all post-marketing AEs.

AE information will be collected as shown in Figure 2.

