### **5.3 Efficacy, Pharmacokinetic and Safety Assessments/Variables**

#### **5.3.1 Efficacy and Safety Measurements Assessed and Flow Chart**

Safety data will be collected in the form of AEs, vital signs, physical examination results, and clinical laboratory tests throughout the treatment period. AEs will be collected for all subjects up to 70 days after the last study drug injection of ADA, or until the subject begins use of commercial ADA, whichever comes first.

The visit window for all scheduled study visits is  $\pm$  3 days for all visits following the Baseline study visit. If a subject has an out of window visit, the next visit should occur as originally scheduled based on the first date of study drug administration (Baseline visit).

All study data will be recorded in the source documents and on the appropriate eCRF. Study procedures will be performed as summarized in the visit schedule presented in [Table 1](#).

**Table 1.** Study Activities

Activity	Pre-screening (>Day -35)	Screening (Day -35 to -3)	Day -0/ Baseline t	Week 8 +/- 3 days	Week 16 +/- 3 days	Week 24/ET +/- 3 days	70-Day F/U a	Unsch. Visit b
Satisfaction questionnaire- Investigator		X		X	X	X		
Informed Consent	X c	X						
Inclusion/Exclusion criteria		X	X					
Medical and Surgical History		X	X					
Alcohol and Nicotine Use		X						
Physical Exam d		X	X	X	X	X	X	
12-Lead ECG		X e						
Chest X-Ray		X f						
TB testing		X g, h						
Vital Signs/Weight/Height i, j		X	X	X	X	X	X	X k
Concomitant medication		X	X	X	X	X		
Hematology		X	X l	X	X	X		
Chemistry		X	X l	X	X	X		
Urinalysis		X	X l	X	X	X		
HBV and HCV screening		X						
HIV		X m						
Pregnancy Test		X n	X o	X o	X o	X o		

ANA/dsDNA		X					
Serum samples for PK (ADA)			X	X	X	X	
Hs-CRP			X			X	
ADA wash-out (for subjects on ADA 40 mg once weekly) p	X						
Satisfaction questionnaire-Subject		X		X	X	X	
PASI evaluation	X		X	X	X	X	
Physicians Global Assessment of Ps (PGA)	X		X	X	X	X	
DLQI		X	X	X	X	X	
Body Surface Area (BSA)	X		X	X	X	X	
Monitor Adverse Events q,r		X	X	X	X	X	
Dispense Study Drugs s		X	X	X	X	X	
Perform drug accountability			X	X	X	X	
Subject dosing diary dispensing			X				
Subject dosing diary review				X	X	X	

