### **Adverse Events**

AEs will be assessed at every study visit from the first dose of study medication through to Week 24 study visit, and during the 70-day safety phone call after the last dose of ADA (or until the subject begins use of commercially available ADA, whichever comes first). In addition, all serious adverse events (SAEs) will be captured from the time the subject signs the Informed Consent Form through study completion or Premature Discontinuation and at the 70-day safety follow-up. Any new AEs/SAEs reported during the 70-day follow-up period should be submitted to AbbVie. The 70-day safety follow-up phone call

will be recorded in source documents only and confirmation of the contact will be faxed to AbbVie (Refer to Section [5.4.1](#) and [Appendix G](#) for additional information).

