**Please contact all Subjects 70 days following last study drug injection (ADA)**

---

Date of Call/Visit: \_\_\_\_\_

- Call not needed as subject is continuing on commercial adalimumab.
- Lost to Follow-Up (Please check this box if subject was not willing to provide any follow-up information or you were unable to speak to the subject following at least one attempt).
- No Events Reported
- AE/SAE Reported

List any Adverse Events (AE) and/or Serious Adverse Events (SAE) that occurred since the subject was last seen in clinic for this study. Please document all adverse events on a 500 AE CRF in the EDC system. (Please report all SAEs to AbbVie within 24 hours of being made aware of the event). **In addition, please note stop dates to any adverse events that were ongoing at the last study visit.**

---

---

---

---

---

---

---

---

**Please fax this form to AbbVie at** [REDACTED]

**Appendix H. Adalimumab injection instructions****Subject Injection Instructions****0.8 mL dose****(Administered as a single dose Pen or pre-filled syringe)****Protocol W14-406****Tables of Contents**

Dosing Schedule

General Information

Injection Procedures

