7.2 Medical History

Medical history will be summarized using body systems and condition/diagnosis as captured on the eCRF. The body systems will be presented in alphabetical order and the conditions/diagnoses will be presented in alphabetical order within each body system. The number and percentage of subjects with a particular condition/diagnosis will be summarized. Subjects reporting more than one condition/diagnosis within a body system will be counted only once for that body system.

7.3**Prior Treatment and Concomitant Medications**

The number and percent of subjects who received a prior or concomitant medication will be tabulated by the generic name assigned by the World Health Organization (WHO) Dictionary.

A prior medication is defined as any medication taken prior to the maximum date of either the first dose of study ADA or the first dose of MTX during the study. A concomitant medication is defined as any medication that started prior to the aforementioned date and continued to be taken after the maximum date of either the first dose of study ADA or the first dose of MTX or any medication that started on or after the date of the first dose of study drug, but not after the last study ADA dose date during the study.

Prior Ps treatment received and discontinued (including reason for discontinuation) prior to screening will be summarized as well.

7.4**Protocol Deviation**

Number and percentage of subjects who reported at least 1 of the following protocol deviation categories will be provided:

- Inclusion/exclusion criteria deviations
- Developed withdrawal criteria but was not withdrawn
- Received wrong treatment or incorrect dose
- Received excluded concomitant treatment

7.5**Inclusion/Exclusion Criteria**

Number and percentage of subjects who did not meet inclusion/exclusion criteria will be reported.

8.0**Patient Disposition**

The summary of subject disposition for the ITT Population will include:

- Number of subjects in the ITT population
- Number and percentage of subjects who complete the entire study
- Number and percentage of subjects who prematurely discontinue from study
- Number and percentage of subjects who remain on ADA/MTX combo after completion from study
- Number and percentage of subjects who remain ADA only after completion from study

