11.2.1 Treatment-Emergent Adverse Events

Treatment-emergent adverse events (TEAE) are defined as following:

TEAEs are defined as any event with an onset date that is on or after the maximum date of either the first dose of study ADA or the first dose of MTX and no more than 70 days after the last study ADA injection during the study.

If an incomplete onset date is collected for an adverse event, the event will be assumed to be treatment-emergent unless there is other evidence that confirms that the event is not treatment-emergent (e.g., the event end date is prior to the study drug start date).

Adverse event data will be summarized and presented using the Medical Dictionary for Drug Regulatory Activities (MedDRA[®]) system organ class (SOCs) and preferred terms (PTs).

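### Active AE follow-up stops early for subjects who continue ADA, but the SAP counts TEAEs to 70 days after last study ADA for everyone, so subject percentages pool unequal follow-up

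*Protocol*

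**What the plan says.** The documents give two different end points for AE collection.

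**Cut short for subjects who continue ADA**
- Protocol 5.3.1: AEs are collected for 70 days after the last study ADA injection "or until the subject begins use of commercial ADA, whichever comes first". The Adverse Events paragraph of 5.3.1.1 has the same limit.
- Protocol 6.1.4 and Table 1 note a: subjects are contacted at about 70 days, "except those subjects that continue on ADA therapy after the end of study participation". Section 6.1.4 adds "These subjects are not required to complete the 70-day follow-up" and that "any new AEs should be reported through the mechanism used for all post-marketing AEs".
- Appendix G: the form has a box reading "Call not needed as subject is continuing on commercial adalimumab".
- SAP 4.2 repeats the exception.

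MTX status appears in none of these.

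**Seventy days with no exception**
- Protocol synopsis (Statistical Methods, Safety) and 8.1.5, for all AEs.
- Table 1 note q for AEs and note r for SAEs.
- The first sentence of 6.1.4, counted from discontinuation of study drugs.
- SAP 11.2.1: a TEAE is an event starting "no more than 70 days after the last study ADA injection during the study", for every subject.

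Subjects who stop MTX and keep ADA are foreseen. The synopsis leaves continuation of each drug to the Investigator separately, and SAP 8.0 plans a row for "Number and percentage of subjects who remain ADA only after completion from study". Protocol 5.3.1.1 says that the follow-up call "will be recorded in source documents only", with confirmation of the contact faxed to the sponsor.

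**The concern.** SAP 5.1 uses the whole Safety Population for safety analyses, and SAP 11.1 does not impute missing safety data. A subject whose AEs were no longer solicited therefore stays in the denominator and counts as event-free for the unobserved days. Two kinds of subject share one percentage: those asked about AEs for the full 70 days after last study ADA, and those asked for about 14.

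The waiver depends on ADA alone, so it also reaches subjects who have just stopped MTX. MTX is the drug this study adds, and Protocol 3.2 names it as a source of added risk. For these subjects the trial has almost no solicited AE information after the last MTX dose, while the SAP table is labelled as if it had.

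**Working it through.** **Inputs**
- Last ADA dose at Week 22 and last MTX dose at Week 23 (Protocol Table 1, note s).
- Nominal Rx Day = 7 × week + 1 (SAP 6.4, Tables 4 to 6).
- TEAE window ends 70 days after last study ADA (SAP 11.2.1).
- Assumption: the subject completes, and commercial ADA starts at Week 24, when the next every-other-week dose would fall.

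**Plan's own days, reproduced**
- Week 22: 7 × 22 + 1 = Day 155
- Week 23: 7 × 23 + 1 = Day 162
- Week 24: 7 × 24 + 1 = Day 169

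All three agree with the SAP tables.

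**Length of the gap**
- End of TEAE window: 155 + 70 = Day 225.
- Solicited after last ADA: 169 − 155 = 14 days. Not solicited: 225 − 169 = 56 days, and 56/70 = 80%.
- Window days after last MTX: 225 − 162 = 63. Solicited: 169 − 162 = 7. Not solicited: 56/63 = 89%.
- Share of the whole window: 56/225 = 25%.

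**Effect on the SAP's subject percentages (illustration)**

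The documents give neither the share of subjects waived nor the AE hazard. Assume a constant hazard with 20% having an event per 70 days, everyone else reached, and no post-marketing report entered in the trial database.
- Full window: 1 − 0.8^(225/70) = 51.2%
- Observed only to Day 169: 1 − 0.8^(169/70) = 41.7%
- 20% waived: 0.8 × 51.2 + 0.2 × 41.7 = 49.3%
- 80% waived: 0.2 × 51.2 + 0.8 × 41.7 = 43.6%

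The same model with other true full-window values gives these reported percentages:

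| True % | 25% waived | 50% | 75% | 100% |
|---|---|---|---|---|
| 50 | 47.6 | 45.3 | 42.9 | 40.6 |
| 10 | 9.4 | 8.8 | 8.2 | 7.6 |

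The shortfall is 2.4 to 9.4 points at a true 50% and 0.6 to 2.4 points at a true 10%.

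**Rate per 100 patient-years**

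SAP 11.2.1.8 divides by study drug exposure. For a completer, SAP 9.0 gives ADA exposure of 155 − 1 + 14 = 168 days. Under constant hazard the ratio of reported to true rate is 225/168 = 1.34 if nobody is waived and 169/168 = 1.01 if everybody is. This rate is not understated, although its numerator and denominator cover different periods.

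**The case against.** **The waiver is deliberate, and AEs are not lost.** Section 6.1.4 sends new AEs to post-marketing reporting. Table 1 note r states SAE collection to 70 days without exception, 6.1.6 collects pregnancies to 150 days, and the Week 24 visit covers the first 7 days after last MTX. This stands against the stronger reading that harm after stopping goes uncollected. The documents support only that AEs are not actively solicited and not assured to reach the trial database. For SAEs the protocol conflicts with itself: note r has no exception, but 5.3.1.1 captures late SAEs at the follow-up contact that is waived. An understated SAE percentage is therefore possible, not established.

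**The bias could look much larger than it is.** A reader might work on the 70-day tail alone. A waived subject then shows 1 − 0.8^(14/70) = 4.4% instead of 20%, and the pooled figure is 0.8 × 20 + 0.2 × 4.4 = 16.9% with 20% waived, or 0.2 × 20 + 0.8 × 4.4 = 7.5% with 80% waived. The SAP plans no such table. Its table starts at first dose, where the same hazard at 80% waived gives 43.6% against 51.2%, a relative shortfall of about 15%.

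**Continuation status is partly known.** SAP 8.0 tabulates it for completers, and Appendix G has boxes for waived and lost and requires AEs to be entered in EDC. So it is too strong to say that an absent event can never be told from an unasked question. However, SAP 8.0 covers status after completion only, no commercial ADA start date is specified, and call status need not be in the database.

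**The study is small, single-arm and descriptive.** No between-arm comparison can be biased, and no safety tests are planned. That limits the consequence but does not make the TEAE window match the data behind it.

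**Conclusion.** The point holds in this form: the protocol disagrees with itself on when AE collection ends, and the SAP's TEAE window runs past solicited collection for subjects who continue ADA. For a completer who starts commercial ADA at Week 24 the gap is 56 of 70 days, or 56 of the 63 window days after last MTX. Subject-level percentages can only equal or fall below the full-window value. The patient-year rate does not share that direction.

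The gap in days follows from the documents and the Week 24 assumption. The effect on percentages does not: 49.3% to 43.6% against 51.2% rests on an assumed hazard and an assumed 20% to 80% waived. A reader might also infer that subjects who stop MTX are where late harm would appear. The documents give no evidence on that, and the point does not need it.

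**What to change.** 1. **Reconcile the protocol** on when AE and SAE collection ends: synopsis (Safety), 5.3.1, Table 1 notes a, q and r, 5.3.1.1, 6.1.4, 8.1.5 and Appendix G. State explicitly what applies to subjects who stop MTX but continue ADA. The sponsor decides the rule. Section 5.4.1 should be checked too: it refers to 5.1 for when the call is not required, and the text of 5.1 contains no such rule (its figure was not available for this check).
2. **Split the table in SAP 11.2.1**, with 8.1.5 and the synopsis changed to match. Tabulate on-treatment TEAEs from first dose to the Week 24/early termination visit. Tabulate post-treatment AEs separately, up to the earliest of 70 days after last study ADA, start of commercial ADA, or last contact. Include only subjects actually followed, by continuation status (ADA and MTX, ADA only, neither). The first period is still not fully observed in everyone: early terminators are seen only to their termination visit, and some may be lost. The table should say so.
3. **Enter on the eCRF** the Appendix G call status (done, waived, lost) and the commercial ADA start date.

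Cost: a changed TEAE definition in both documents, one extra table split and two small eCRF fields. Post-treatment results will rest on fewer subjects. These analysis and data changes need no new visits.

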**Figure 2. Adverse Event Collection**

### **6.1.5 Adverse Event Reporting**

In the event of an SAE, and additionally any non-serious event of malignancy in subjects 30 years of age and younger, whether related to study drug or not, the physician will notify the AbbVie Pharmacovigilance Team within 24 hours of the site being made aware of the SAE by entering the SAE or non-serious events of malignancy in subjects 30 years of age and younger into the RAVE® electronic data capture (EDC) system. SAEs or non-serious events of malignancy in subjects 30 years of age and younger, that occur prior to the site having access to the RAVE® EDC system or if RAVE® is not operable should be documented on the SAE non-CRF forms and e-mailed (preferred route) or faxed to the

Adalimumab/Methotrexate  
W14-406 Protocol  
Amendment 2, 22 April 2016

---

AbbVie Clinical Pharmacovigilance Team within 24 hours of the site being made aware of the AE.

#### **6.1.6      Pregnancy**

Pregnancy in a study subject or a partner of study subject must be reported to AbbVie within 1 working day of the site becoming aware of the pregnancy. Subjects who become pregnant during the study must be discontinued (Section [5.4.1](#)).

Pregnancies in study subjects and their partners will be collected from the date of the first dose through 150 days following the last dose of study drug.

Information regarding a pregnancy occurrence in a study subject or a study subject's partner and the outcome of the pregnancy will be collected.

In the event of pregnancy occurring in a subject's partner during the study, written informed consent from the partner must be obtained prior to the collection of any such information.

Pregnancy in a study subject is not considered an AE. However, the medical outcome of an elective or spontaneous abortion, stillbirth or congenital anomaly is considered a SAE and must be reported to AbbVie within 24 hours of the site becoming aware of the event.

#### **6.1.7      Toxicity Management**

Subjects who develop a new infection while undergoing treatment with ADA and MTX should be monitored closely. Administration of study ADA injections and/or oral MTX should be interrupted if a subject develops an infection requiring intravenous (IV) anti-infective treatment or if an infection meets the definition of "serious" (see Section [6.0](#) for definitions). Study medication may be restarted once the Investigator determines that the

infection has been successfully treated. Otherwise prohibited concomitant medications may be given if medically necessary. Prior to any prohibited medication use, every attempt should be made to contact the AbbVie Medical Monitor for direction on re-introduction of ADA and MTX therapy after prohibited medication administration; however, these communications should not delay the administration of any necessary medication(s), study-prohibited or otherwise, to the subject.

If the subject must undergo elective surgery, the study ADA injections and oral MTX must be interrupted 2 weeks prior to the surgery. If the subject must undergo emergency surgery, the study ADA injections and oral MTX must be interrupted at the time of the surgery. ADA and oral MTX can recommence at least 2 weeks after surgery once the physician has examined the surgical site and determined that it has healed and there is no sign of infection. If any subject needs to skip more than two ADA doses or two weekly doses of MTX (consecutive or intermittent) over the course of the study, even if for the situations described above, further follow-up on the subject's study participation should be discussed with the AbbVie Study designated Physician.

